## 10.2 Secondary Efficacy Analyses

### 10.2.1 Secondary Analyses of Primary Efficacy Endpoint

Several sensitivity analyses are performed to assess how alternative approaches to missing data and model assumptions affect the conclusions of the analysis of the primary outcome:

1. Analysis of the primary efficacy variable as described in section 10.1 is performed using the PP population.
2. Analysis of the primary efficacy variable described in section 10.1 with the m-ITT analysis set except that HRCT fibrosis scores in the lobe of maximal involvement (QLF-LM) at screening is added as a covariate.
3. Analysis of the primary efficacy variable described in section 10.1 with the m-ITT analysis set except that baseline mRSS is added as a covariate.
4. Analysis of covariance (ANCOVA) is used to analyze the change of FVC-% from baseline to month 18 (that is, FVC-% at month 18 - FVC-% at baseline). The model includes the treatment group, baseline FVC-% and prior MMF therapy.
5. In addition to the assessment of the overall trajectory of pulmonary response which integrates the timing of the onset of response and the overall magnitude of effect at 18 months, we evaluate the individual components of this response. This is accomplished by using the linear mixed effects model with same covariates described for the analysis of primary efficacy variable and provide adjusted estimates of change from baseline in FVC-% for each treatment group and treatment difference for each time point (e.g., 3, 6, 9, 12, 15 and 18 months).
6. Descriptive statistics are provided to assess more granular changes in FVC-% by treatment adherence (e.g., premature discontinuation of study treatment prior to 3, 6, 9, 12, 15 and 18 months) in the completers population.

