10.5.2 Assumptions

Based on these available data, the following assumptions were used to generate clinical outcome scenarios for the potential response of FVC-% over time for both the control arm (MMF+Plac) and the experimental arm (MMF+PFD) of SLS III:

- 1) Data from SLS I and II were used as the best available data to estimate the standard deviation of the FVC-% values at different times in the study and the mean change in FVC-% at 3, 6, 9, 12, 15 and 18 months were assumed to follow a multivariate normal distribution, with equivalent variances in the two treatment groups.
- 2) In the same manner, data from the II study was used to inform the estimated impact of prior therapy with MMF, occurring prior to randomization, on the expected mean change in FVC-% and the variance of the FVC-% values at different times after randomization.
- 3) We measured the correlation structure over time for repeated measurement of the FVC-% in individual subjects participating in the SLS I study and applied that to the prediction of outcomes for SLS III. As one might assume, correlation between measurements taken at closer intervals is greater than measurements taken farther apart and from SLS I data the correlations among outcomes 3 months apart was 0.866, 6 months apart was 0.834, and 9 months apart was 0.802.
- 4) Treatment with cytotoxic therapy (MMF or CYC) is associated with an initial period of deteriorating lung function during the first 3-6 months of treatment that appears due to the required titration of cytotoxic medication over several months and the relatively slow clearing of existing immune mediators that drive inflammation and tissue destruction. This initial loss of lung function can average from -0.25% to -2.5%.
- 5) After an initial 3-6 month period that is associated with a relative decline of lung function, continued treatment with cytotoxic therapy is associated with a relative improvement in lung function over time that ranges from approximately +2.0 to +3.0% at 12 months and from approximately +3.0 to +5.0% at 18 months.

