10.5.3 Defining the Primary Study Outcome

[figure not shown]
The primary aim of the study is to compare the impact of combining PFD and MMF in the experimental arm with that of MMF plus Plac in the control arm on pulmonary function during the 18-month double-blind period. The primary endpoint is change from baseline in the mean forced vital capacity, measured as the percentage of the age-, height-, gender- and race-adjusted predicted value (FVC-%) over the course of the 18-month double-blind treatment period. FVC is measured at baseline (pre-treatment) and then quarterly after treatment begins during the treatment period (i.e., months 3, 6, 9, 12, 15 and 18). Participants are required to have FVC-% \leq 85% at screening.

10.5.4 Clinical Trial Scenarios and Simulations to Estimate Study Power in Treatment Naïve Patients

Two outcome scenarios were considered based on the two potential mechanisms of action by which the addition of PFD might improve the response to treatment with MMF alone. Both scenarios assume that the average response pattern to MMF alone (the control arm) would approximate the average response pattern to cytotoxic therapy observed from SLS II. In that study, the overall improvement from baseline in the FVC-% was approximately 3.0% at the 12 month time point and 4.25% at 18 months. Two different response scenarios were then proposed to represent the range of possible responses in patients treated with combined MMF+PFD (the experimental arm).

- **In Scenario 1**, it is assumed that treatment with PFD is associated with an early slowing of the decline in lung function normally observed during the first 3-6 months of cytotoxic therapy and that there is only a small additive effect of PFD to the later improvement in lung function. The collective result is a 2.5% greater response to treatment at 12 months in the experimental versus control arms and this difference between the groups remains the same for the duration of the 18-month study.
- **In Scenario 2**, it is assumed that treatment with PFD is associated with both an early slowing of the decline in lung function and a definite additive effect on the overall improvement in FVC-% that continues throughout the entire treatment period. The collective result is a 3.125% greater response to treatment at 12 months in the experimental versus control arms which continues to slowly increase to a final 3.25% difference between the two groups at 18 months.

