## 10.1 Primary Efficacy Analysis

The primary endpoint is change from baseline in the mean forced vital capacity, measured as the percentage of the age-, height-, gender- and race-adjusted predicted value (FVC-%) over the course of the 18-month treatment period, as reported quarterly (i.e., months 3, 6, 9, 12, 15 and 18). The primary efficacy analysis tests the null hypothesis that the differences between the MMF+PFD and MMF+Plac is zero. The primary analysis of the primary efficacy endpoint uses the m-ITT analysis set. The endpoint is analyzed using a linear mixed model with participant-month in the study (3, 6, 9, 12, 15, 18) as the unit of analysis and the change from baseline in FVC-% as the outcome, with terms for baseline FVC-%, treatment group, month, the interaction of month and treatment group, and prior MMF therapy (stratification factor: naïve, >0 to  $\leq$ 3 months, and >3 months to 6 months), as fixed covariates. Study participant is treated as a random effect to account for the correlation of outcomes over time within a participant.

The model is summarized below.

$$FVC\%-_{it} = \mu_0 + \mu_1 \text{TRT}_i + \mu_2 \text{MONTH}_{it} + \mu_3 \text{TRT}_i \times \text{MONTH}_{it} + \mathbf{x}_i' \boldsymbol{\beta} + \epsilon_{it},$$

where  $FVC\%-_{it}$  is the change of FVC-% from baseline at time  $t$  for patient  $i$  (that is, FVC-% at time  $t$  - FVC-% at baseline),  $i = 1, \dots, 51$ ;  $t = 1, \dots, 6$  (corresponding to 3, 6, 9, 12, 15 and 18 months).  $\text{TRT}_i$  is treatment group (equal to 1 for the PFD and MMF and 0 for Plac and MMF) for patient  $i$ .  $\text{MONTH}_{it}$  is the study month at time  $t$  for patient  $i$ . Two dummy variables for prior MMF therapy (stratification factor: naïve, >0 to  $\leq$ 3 months, and >3 months to 6 months), and baseline FVC-% for subject  $i$  are included in a vector  $\mathbf{x}_i$  of 3 covariates ( $x_1, x_2, x_3$ ) and associated fixed effects are stored in vector  $\boldsymbol{\beta} = (\beta_1, \beta_2, \beta_3)$ . We assume that residual errors  $\epsilon_{it}$  ( $t = 1, \dots, 6$ ) for subject  $i$  are normally distributed with zero mean and 6x6 general/unstructured variance-covariance matrix.

In the context of the primary analysis of the primary endpoint, we are interested in parameter  $\mu_3$ , representing the trajectories of the primary endpoint adjusted for stratifying variables and baseline covariates.

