The model generates adjusted estimates of change from baseline in the FVC-% for each treatment group and month, and an F-test is used to test the hypothesis that the mean change from baseline during the treatment period differs between the two treatment groups.

The model-based adjusted mean change from baseline in FVC-% will be presented graphically by treatment group by study month, with 95% confidence intervals (CIs) provided at each month.

Analysis	Primary Analysis of the Primary Endpoint: mean FVC-% change from baseline during the treatment period differs between the two treatment groups
Analysis Set	mITT Population
Methods	Linear mixed model for repeated measures with correlated errors
Dependent Variable	Change of FVC-% measured at 3, 6, 9, 12, 15 and 18 months (FVC-% at x months – FVC-% at baseline, where x=3, 6, 9, 12, 15 and 18)
Model	Fixed effects: 
 
• Treatment
 
• Study month
 
• Interaction of treatment and study month
 

	
 
• Stratifying variable: prior MMF therapy with 3 categories
 
• Baseline FVC-%
 

Results	
 
• Estimates of mean change from baseline in FVC-% during the treatment period (slope) by treatment group and treatment difference
 
• 95% confidence interval for treatment estimates and treatment difference
 
• P-value for treatment difference
 

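### As its equation is written, SAP 10.1 fits change in FVC-% as a straight line in month, so the visit-specific differences (10.2.1 item 5) and the monthly graph would distort the timing of the treatment effect

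*SAP*

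**What the plan says.** **The model.** The SAP 10.1 equation has one coefficient (mu2) on MONTH and one (mu3) on treatment × MONTH. MONTH "is the study month at time" t. Prior MMF is explicitly dummy-coded; month is not, and the covariate vector has room only for two prior-MMF dummies and baseline FVC-%. The section continues: "In the context of the primary analysis of the primary endpoint, we are interested in parameter" mu3, described as "representing the trajectories of the primary endpoint adjusted for stratifying variables and baseline covariates". The Results row lists "Estimates of mean change from baseline in FVC-% during the treatment period (slope) by treatment group and treatment difference".

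**The competing wording.** The same section says: "The model generates adjusted estimates of change from baseline in the FVC-% for each treatment group and month". It describes both a participant random effect and a 6×6 unstructured residual matrix.

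**The reuse.** Item 5 of SAP 10.2.1 takes the treatment difference at each of the six visits from this model: "This is accomplished by using the linear mixed effects model with same covariates described for the analysis of primary efficacy variable".

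**The expected course.** Protocol 10.5.2 expects an initial loss averaging 0.25 to 2.5 points. It then describes recovery: "After an initial 3-6 month period that is associated with a relative decline of lung function", continued cytotoxic therapy brings improvement. Protocol 10.5.4 puts the control arm at about +3.0 at 12 months and +4.25 at 18. In Scenario 1 the arms differ by 2.5 points at month 12 and "this difference between the groups remains the same for the duration of the 18-month study". In Scenario 2 the difference barely grows after month 9.

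**The concern.** The primary hypothesis is a faster and/or larger improvement. A straight line per arm has two free numbers, so the six differences in item 5 are one intercept gap and one slope gap read off at six months. Such a model cannot show arms that separate early and then run parallel, which is the pattern the trial was designed around.

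SAP section 14(g) removed the change-point analysis, so item 5 and the monthly graph are the main remaining model-based view of when the arms separate. The same model also serves SAP 10.2.1 items 1-3, SAP 10.2.2 items 1-3 and SAP section 12 item 1.

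**Working it through.** **Inputs (SAP Table 7.1, same as Protocol Table 10.5.4), months 3, 6, 9, 12, 15, 18**
- Gap, Scenario 1: 0.5, 1.375, 2.25, 2.5, 2.5, 2.5 (mean 1.94).
- Gap, Scenario 2: 0.75, 1.75, 3.0, 3.125, 3.25, 3.25 (mean 2.52).
- SDs: 4.1, 5.1, 6.2, 6.9, 6.2, 6.2.
- Correlations at lags of 3 to 15 months: 0.866, 0.834, 0.802, 0.790, 0.780. The table heads these AR1, but they do not decay geometrically.
- Cumulative dropout: 6.5, 13, 17, 20, 23, 24%.

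**1. The plan's own figures.** Mean dropout is 103.5/6 = 17.25%, so 82.75% of data points remain; the plan says 83%. Power was simulated with 2,500 trials per cell, compound symmetry, categorical month and the 5-df treatment-by-month F-test:

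| Per arm | Sc. 1 simulated | Sc. 1 stated | Sc. 2 simulated | Sc. 2 stated |
|---|---|---|---|---|
| 75 | 82.5% | 82.3% | 95.4% | 95.6% |
| 70 | 78.4% | 78.6% | 94.4% | 92.6% |
| 65 | 75.2% | 76.3% | 92.3% | 91.8% |

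All are within 2 points. The linear mu3 test under compound symmetry gives 87.3% (Scenario 1) and 96.8% (Scenario 2) at 75 per arm. Its rejection rate with no effect was 13.2% in 1,500 trials, so that power is inflated. The sizing is best matched by categorical month.

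**2. Straight line, unstructured covariance.** Let X have columns 1 and month, V be built from the SDs and correlations, and d be the planned gap. The expected fitted gap is X(X′V⁻¹X)⁻¹X′V⁻¹d. With dropout, the two cross-products are summed over the dropout patterns.

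With complete data, the fitted six-visit average weights the visit gaps by 0.678, 0.068, −0.250, −0.350, 0.293, 0.562. In Scenario 1 this is 0.339 + 0.094 − 0.563 − 0.875 + 0.733 + 1.405 = 1.13, against 1.94. Months 9 and 12, where the planned gap is already large, get negative weight.

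| Fitted gap | 3 | 6 | 9 | 12 | 15 | 18 | Mean | Error in mean |
|---|---|---|---|---|---|---|---|---|
| Sc. 1, complete | 0.16 | 0.55 | 0.94 | 1.33 | 1.71 | 2.10 | 1.13 | −42% |
| Sc. 1, dropout | 0.20 | 0.60 | 1.00 | 1.40 | 1.80 | 2.20 | 1.20 | −38% |
| Sc. 2, complete | 0.33 | 0.82 | 1.32 | 1.81 | 2.30 | 2.79 | 1.56 | −38% |
| Sc. 2, dropout | 0.38 | 0.89 | 1.39 | 1.89 | 2.40 | 2.90 | 1.64 | −35% |

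Against the planned gaps, months 3-9 are 49-68% too small, month 12 39-47%, month 15 26-31% and month 18 11-16%. With true AR(1) correlations (0.866 per 3 months) the mean is 28-34% too small.

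The control course is not tabulated visit by visit, so three courses within the stated decline were tried at 4,000 per arm with the covariance estimated. The fitted mean was 0.62-0.66 of the true mean each time.

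**3. Straight line, random intercept.** With complete data this is an ordinary least-squares line. In Scenario 1 the slope is 20.4375/157.5 = 0.130 per month around a mean of 1.94 at month 10.5:
- month 3: 1.94 − 7.5 × 0.130 = 0.96, against 0.5 (+93%)
- month 9: 1.74, against 2.25 (−23%)
- month 18: 2.91, against 2.5 (+16%)

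The mean is exact. In Scenario 2 month 3 is 1.30 against 0.75 (+73%). With dropout, month 3 is overstated by 83% and 65% in the two scenarios, month 9 is understated by about 25%, and the mean by under 2%.

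**4. Categorical month.** The expected visit gaps equal the planned gaps.

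**The case against.** **The text does not clearly commit to a line.** It promises estimates for each group and month, confidence intervals at each month and an unstructured matrix, and the sizing fits categorical month. This stands as evidence of intent. It does not undo an equation with scalar month terms, a single named parameter and a slope label; a programmer could defend either model.

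**A reader might infer that the trial understates its effect by about 40%.** The documents do not support that as a general statement. The figure belongs to the six-visit average under one covariance reading, with the tabulated correlations. It is 11-16% at month 18 and about zero on average under the random-intercept reading, where the month-3 error favours early onset. It also assumes all patients are treatment-naïve. Up to half may have had prior MMF, for whom the plan expects smaller separation; those curves are in a figure that is not reproduced.

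**A reader might infer that the faster-onset objective is wrongly estimated throughout.** It is not. The Kaplan-Meier time to a 3-point improvement (SAP 10.2.2 item 5) and the month-18 ANCOVA (SAP 10.2.1 item 4) do not use the line. They do not replace visit differences, because the first is a responder threshold and the second says nothing about onset.

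**A reader might infer a loss of power.** The simulations show the opposite for the slope test (see the fix).

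**The gain in total error is small at n = 51.** Simulated SEs of the average were 1.32-1.37 (line) and 1.49-1.50 (categorical). With a bias of 0.74-0.96, the line's root mean squared error runs from √(1.32² + 0.74²) = 1.51 to √(1.37² + 0.96²) = 1.67, against about 1.5. This stands for the average; it does not help the shape of the early visit estimates.

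**Conclusion.** The point holds as a specification error with a conditional size. Followed as written, SAP 10.1 forces straight-line means that conflict with its own promise of monthly estimates and with the planned course, and item 5 and the monthly graph would misplace the effect in time. The direction of the early error depends on which covariance statement is applied: too small under the unstructured matrix, too large at month 3 under a random intercept. Month 9 is understated under both.

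The sizes rest on the Table 7.1 gaps for treatment-naïve patients and its SDs and correlations, on dropout unrelated to outcome, and on no baseline-covariate effect. The harm is to estimation and interpretation of onset; the mu3 test itself does not lose power.

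**What to change.** Before unblinding:
1. In SAP 10.1 and every model that reuses it (10.2.1 items 1-3 and 5; 10.2.2 items 1-3; section 12 item 1), declare month a categorical factor with a treatment-by-month-category interaction: six levels, or three for 6-monthly outcomes. Replace the scalar MONTH terms with indicators.
2. Take the visit differences, the average difference and the monthly graph from that model, and remove the slope label from the Results row.
3. State one covariance structure.
4. Name the primary contrast.

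**Cost.** The six-visit models gain eight fixed-effect parameters (four for month, four for the interaction). In simulations of 51 participants, the number indexed in SAP 10.1, the SE of the average difference rose by roughly 10% (1.49/1.37 = 1.09 to 1.50/1.32 = 1.14).

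The primary contrast costs more. At 75 per arm under the unstructured matrix, simulated power is:

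| Primary test | Scenario 1 | Scenario 2 |
|---|---|---|
| mu3 (linear) | 81% | 95% |
| Categorical, visit average | 56% | 79% |
| Categorical, 5-df interaction | 74% | 92% |

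Moving the primary test off mu3 is therefore a separate decision from making the visit estimates categorical. It should be made explicitly, and the change in power disclosed.

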### 10.2.2 Secondary Efficacy Analyses

The m-ITT analysis set will be used in the analyses of secondary endpoints if not otherwise indicated.

1. The linear mixed model as described for the primary analysis of the primary endpoint is performed to compare the two treatment groups for the change from baseline to 18 months, measured by

3-month intervals, in the following outcomes. The model is adjusted by treatment, study month, interaction of treatment and study month, prior MMF therapy and baseline outcome. For FVC (measured in ml), the model also includes age (measured as a real number and not an integer), height, sex and race (i.e., the same variables used in the percent predicted equations). The model generates adjusted estimates of the change from baseline for each treatment group and month, and an F-test is used to test the hypothesis that the mean change from baseline during the treatment period differs between the two treatment groups. The model-based adjusted mean change from baseline will be presented graphically by treatment group and study month, with 95% confidence intervals (CIs) provided at each month.

- a. Hemoglobin-adjusted DLCOHb-%
  - b. mRSS
  - c. FVC (in ml)
  - d. SGRQ: Total score, Symptoms, Activity, Impacts
2. The linear mixed model as described for the primary analysis of the primary endpoint is performed to compare the two treatment groups for the change from baseline to 18 months, measured at 3-month intervals, in dyspnea. The model is adjusted by treatment, study month, interaction of treatment and study month, prior MMF therapy, and BDI. The model generates adjusted estimates of TDI for each treatment group and month, and an F-test is used to test the hypothesis that the mean change from baseline during the treatment period differs between the two treatment groups. The model-based adjusted mean TDI will be presented graphically by treatment group and study month, with 95% confidence intervals (CIs) provided at each month.
3. The linear mixed model as described for the primary analysis of the primary endpoint is performed to compare the two treatment groups for the change from baseline to 18 months, measured at 6-month interval, in SHAQ. The model is adjusted by treatment, study month, interaction of treatment and study month, prior MMF therapy and baseline SHAQ. The model generates adjusted estimates of the change from baseline in SHAQ for each treatment group and month, and an F-test is used to test the hypothesis that the mean change from baseline during the treatment period differs between the two treatment groups. The model-based adjusted mean change from baseline in SHAQ will be presented graphically by treatment group and study month, with 95% confidence intervals (CIs) provided at each month. SHAQ includes:
  - a. HAQ-DI without Aids/Devices: Total score
  - b. SHAQ-DI VAS assessing burden of pain, burden of digital ulcers, Raynaud's, GI involvement, breathing, and overall disease
4. For each HRCT outcomes – QLF-LM, QLF-WL, QILD-LM, QILD-WL, and HRCT-TLC, analysis of covariance (ANCOVA) is used to analyze the change of the HRCT outcome from screening to month 18. The model includes the treatment group, HRCT outcome at screening, and prior MMF therapy.
5. For time (in months) required to achieve a 3.0% (absolute) or greater improvement from baseline in the FVC-% over the 18-month treatment period, Kaplan-Meier methods are used to graphically present treatment group differences. The median time to event, with 95% CIs, will be presented by treatment group, and a stratified (by prior MMF therapy) log-rank test p-value are presented. The time (in months) is defined as the time from baseline until the time of the first change of FVC-%

from baseline is greater or equal to 3%. Participants are censored at date of FVC-% collected at month 18 visit or at the last date of FVC-% collected if the participants permanently discontinued study.

6. Logistic regression is performed to evaluate the proportion of participants who achieve greater than a 5% improvement from baseline in the FVC-% over the 18-month treatment period. The model includes treatment group, baseline FVC-%, and prior MMF therapy as covariates. A participant with FVC-% at 18 months minus FVC-% at baseline that is greater than 5% defines a 5% improvement or greater. . The odds ratio with corresponding 95% CI is presented; the p-value for the test of treatment group differences is also presented.
7. Box plots are used to summarize the frequency distributions of changes from baseline to 18 months by treatment group for key secondary endpoints: Hemoglobin-adjusted DLCOHb-%, mRSS (for all patients and for diffuse cutaneous scleroderma [dcSSc] patients), SGRQ (total score, Symptoms, Activity and Impacts subscores), HAQ-DI without aids/devices score, and Scleroderma-HAQ-DI visual analogue scales (VAS) scores. A box plot is also used to summarize the frequency distribution of TDI during the study period.
8. A frequency table and bar chart are used to show the frequency distribution of the change of FVC-% from baseline to month 18 with a 5% increment (e.g., improved by up to 5%, from 5% to <10% and from 10% to <15% or worsened by up to 5%, from 5% to <10%, and from 10% to <15%), overall and in each treatment group in the completers population, and separately for those who completed the treatment period and those who prematurely discontinued treatment but returned for the 18-month FVC-%.
9. A frequency table is used to show the frequency distribution of the change of FVC-% from baseline to month 18 in negative responders ( $\leq -3\%$ ) and stable ( $> -3\%$  to  $< 3\%$ ) overall and in each treatment group in the completers population, and separately for those who completed the treatment period and those who prematurely discontinued treatment but returned for the 18-month FVC-%.
10. A frequency table is used to show the frequency distribution of the change of FVC-% from baseline to month 18 in responder ( $>0$ ) and non-responder ( $\leq 0$ ) overall and in each treatment group in the completers population, and separately for those who completed the treatment period and those who prematurely discontinued treatment but returned for the 18-month FVC-%.
11. A frequency table and bar chart are used to show the frequency distribution of the change of mRSS from baseline to month 18 categorized in 4 points increments: worsen (1 to 4,  $\geq 5$ ), no change ( $=0$ ), and improved ( $\leq -13$ ,  $-12$  to  $-9$ ,  $-8$  to  $-5$ ,  $-4$  to  $-1$ ) overall and in each treatment group in the completers population, and separately for those who completed the treatment period and those who prematurely discontinued treatment but returned for the 18-month mRSS. A frequency distribution of the change of mRSS is also shown in patients with dcSSc in the completers population. The proportions of participants with improved ( $< -5$ ), no change ( $-5$  to  $5$ ), and decreased ( $> 5$ ) in the change from baseline in mRSS, overall and in each treatment group, are also presented.

12. A frequency table and bar chart are used to show the frequency distribution of the TDI at month 18 categorized as improved by 1-3, 4-6 and 7-9 points, no change (0), and worsened by 1-3, 4-6 and 7-9 points, overall and in each treatment group in the completers population, and separately for those who completed the entire treatment period and those who prematurely discontinued treatment but returned for the 18-month TDI. The proportions of participants with improved ( $>0$ ), no change, and deterioration ( $<0$ ), overall and in each treatment group, are also presented.

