## **7 Sample Size**

An initial sample size target of 150 participants (up to 190 consented and screened subjects to achieve 75 randomized per treatment group) was identified based on recent clinical trial experience and logistical considerations including the number of clinical centers with appropriate leadership and infrastructure to be considered as state of the art for treating SSc-ILD. Statistical analysis, using a clinical trials simulation approach, was then employed to estimate the power to detect various treatment effects on the primary endpoint with a two-sided Type I error of 5% and an 18-month attrition estimate of 24%.

[figure not shown]
Data from the SLS I and II clinical trials were used to estimate the baseline characteristics of the proposed study population and their response over time to treatment with MMF, including the impact of prior treatment with MMF (occurring prior to study randomization), on the predicted course of lung function changes over time. Note that SLS III will employ essentially the same patient recruiting centers and investigators as those that participated in the prior studies (with some new additions) and that the enrollment criteria have been relatively conserved over time to assure reproducibility. Furthermore, both the control arm and experimental arm of the proposed study will be treated with a course of cytotoxic therapy that is essentially identical to that reported from the SLS I and II studies. For the impact of PFD, safety and tolerability data from the LOTUSS trial and outcome data from studies in which PFD was used to treat IPF were considered informative.

Two outcome scenarios were considered based on the two potential mechanisms of action by which the addition of PFD might improve the response to treatment with MMF alone. Both scenarios assume that the average response pattern to MMF alone (the control arm) would approximate the average response pattern to cytotoxic therapy observed from SLS II. In that study, the overall improvement from baseline in the FVC-% was approximately 3.0% at the 12 month time point and 4.25% at 18

months. Two different response scenarios were then proposed to represent the range of possible responses in patients treated with combined MMF+PFD (the experimental arm).

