##### f. Change Analyses of Secondary Endpoints

Due to small sample size, instead of considering binary secondary endpoints and using logistic regression, we consider clinically meaningful cutpoints and using the frequency table and bar chart to demonstrate the frequency distribution of the secondary endpoints.

PROTOCOL:

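### The >5-point FVC-% responder analysis is a four-slope logistic regression with no small-sample method in a trial of 51, so a true odds ratio is overstated on average by a modest amount

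*SAP*

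**What the plan says.** On the responder endpoint, SAP 10.2.2 item 6 says: "Logistic regression is performed to evaluate the proportion of participants who achieve greater than a 5% improvement from baseline in the FVC"-%. It defines a responder by "FVC-% at 18 months minus FVC-% at baseline that is greater than 5" percentage points. On covariates it says: "The model includes treatment group, baseline FVC-%, and prior MMF therapy as covariates". SAP 10.1 describes "prior MMF therapy with 3 categories", so there are four slopes and an intercept. On reporting, item 6 says: "The odds ratio with corresponding 95% CI is presented", together with a p-value. It gives no estimation method beyond logistic regression and no rule for separation or non-convergence. The default analysis set in 10.2.2 is m-ITT.

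The primary model in SAP 10.1 runs over 51 patients, against the 150 planned in Section 7. The SAP gives no count of participants with a month-18 FVC-%.

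Section 14f explains the frequency tables of items 8 to 12 with the words "Due to small sample size, instead of considering binary secondary endpoints and using logistic regression". Item 6 keeps logistic regression. Protocol 10.4.3.1 had listed treatment group, site and prior MMF as covariates for dichotomous outcomes. Item 6 has baseline FVC-% in place of site.

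**The concern.** Maximum-likelihood logistic regression is biased away from an odds ratio of 1 when there are few participants per coefficient. A sparse category whose members all share one outcome also sends its coefficient to infinity. The planned trial was large enough for neither to matter much. At 51 participants both can occur.

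Item 6 is the only FVC-% responder analysis for which the SAP reports an odds ratio, interval and p-value. If there is a real effect, the reported odds ratio will on average be too large. If a prior-MMF stratum is perfectly predicted, someone must decide after unblinding whether to drop the covariate, pool strata or change the method, because the SAP names no response.

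**Working it through.** **Reproducing the planning figures (SAP Table 7.1).** The documents give no power or sample size for this responder endpoint, so the primary-endpoint figures were checked to confirm that the inputs are read correctly.
- 75, 70 and 65 × 0.76 = 57, 53.2 and 49.4 per arm (stated 57, 53, 49).
- Mean retention over six visits = (93.5 + 87 + 83 + 80 + 77 + 76)/6 = 82.75% (stated 83%).
- Power was simulated (1,000 trials per setting) with the tabulated differences, SDs, correlations and dropout, and a compound-symmetry mixed model with treatment-by-month F-test. Scenario 1 gave 81.1, 79.8 and 75.4% (stated 82.3, 78.6, 76.3). Scenario 2 gave 94.6, 92.1 and 93.4% (stated 95.6, 92.6, 91.8). All six agree within 2 points.

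**Number analysed.** SAP Section 7 plans with "an 18-month attrition estimate of 24" percent: 51 × 0.76 = 38.8, about 39. This is a projection. The upper limit is 51.

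**Implied responder rates.** Section 7 puts the control improvement at "approximately 3.0% at the 12 month time point and 4.25% at 18" months. The month-18 SD is 6.2 and the differences are 2.5 (Scenario 1) and 3.25 (Scenario 2). With a normal distribution, P(change > 5) = 1 − Φ((5 − mean)/6.2):
- Control, mean 4.25: 1 − Φ(0.121) = 45.2%
- Scenario 1, mean 6.75: 1 − Φ(−0.282) = 61.1%, odds ratio (0.611/0.389)/(0.452/0.548) = 1.91
- Scenario 2, mean 7.5: 1 − Φ(−0.403) = 65.7%, odds ratio 2.32

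**Information per slope at n = 39.** Non-responders are the rarer class: 39 × (1 − (0.452 + 0.611)/2) = 18.3 in Scenario 1 and 39 × (1 − (0.452 + 0.657)/2) = 17.4 in Scenario 2. Divided by four slopes, that is 4.6 and 4.3.

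**Simulated bias.** Each setting used 4,000 data sets with 1:1 arms, item 6's covariates, and separation detected by linear programming. The prior-MMF split and covariate effects are not in the documents and were varied.
- n = 39: log odds ratio inflated by 14 to 19%, and by up to 22% over all runs, including those with prognostic covariates. Example: ln 2.32 = 0.842; 0.842 × 1.174 = 0.988; exp(0.988) = 2.69. For 1.91, ln 1.91 = 0.647; 0.647 × 1.145 = 0.741; exp(0.741) = 2.1.
- n = 51, all observed: 11 to 16%.
- n = 51, missing month-18 values counted as non-response: about 10%.
- n = 114 (2 × 57, as planned): about 4%.
- Null: geometric-mean odds ratio 0.99, rejection rate 6.0%.

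**Bias against imprecision at n = 39.** The 95% interval spans about a 16-fold range, so the standard error is about ln(16)/3.92 = 0.71. The Scenario 2 bias is 0.988 − 0.842 = 0.146, and 0.146/0.71 is about one fifth of a standard error. Power is about 16 to 28%.

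**Divergence at n = 39.** Some coefficient is infinite in about 0.4 to 3% of data sets with a 50/25/25 split, and in about 11 to 28% when one or two strata have about 4 people. The treatment odds ratio itself is infinite in at most 0.1% at the implied rates.

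**Firth penalisation on the same inputs.** The mean treatment log odds ratio is within about 5% of the truth, root mean squared error is roughly 10 to 18% lower, and estimates stay finite under separation.

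**The case against.** The strongest reply is that little depends on this odds ratio. SAP 8.6 makes secondary analyses supportive. SAP 10.2.1 item 4 analyses the same month-18 change by ANCOVA with the same covariates, and 10.2.2 item 8 tabulates it in 5-point bands. Imprecision is a larger limit than the bias, and penalisation does not cure it. All of this stands, and it makes the point minor.

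Item 6 also says only logistic regression, so maximum likelihood is inferred. That stands too, although it is the default reading when SAP Section 9 names SAS and no option is given. Participants who stop drug are asked back at month 18, so 39 may be too low. The bias persists, somewhat smaller, at 51.

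Three stronger readings are tempting, and the documents do not support them:
- **That the analysis fails outright.** What diverges is almost always a prior-MMF coefficient, and the reported treatment odds ratio stays finite. Failure shares of 13% or 38% with a 50/25/25 split need control response rates near 25% or 15%, which appear nowhere in the documents.
- **That the estimate overstates whatever is found.** There is no bias under the null, and under an effect the overstatement is an average.
- **That Section 14f forbids item 6, or that the model was carried over unchanged.** Section 14f is a change summary that lists items 8 to 12, and item 6's covariates differ from the protocol's. What 14f does show is that the SAP cites small sample size as its reason for moving away from logistic regression elsewhere, without saying why item 6 is exempt.

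**Conclusion.** The point holds as a minor one. If there is an effect of the planned size, standard maximum likelihood inflates the treatment log odds ratio by about 14 to 22% on average with about 39 analysed and about 11 to 16% with 51: a true 2.3 is reported on average as about 2.7, or about 2.6 with 51. It leaves a null result unbiased. The SAP has no planned response if a prior-MMF coefficient diverges, and how likely that is depends on stratum sizes that the documents do not give.

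The size rests on normally distributed change with the SAP's mean and SD, on responder rates implied by an all-naïve population, on attrition at the planned rate for the figure of 39, and on assumed strata and covariate effects. SAP 10.2.2 also does not say how an m-ITT participant without a month-18 value is classified, which affects the number analysed.

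**What to change.** In SAP 10.2.2 item 6, keep the endpoint and the covariates. Specify Firth penalised logistic regression for the odds ratio, with a profile-likelihood 95% interval and p-value. Add a clause there or in Section 14f saying why this binary endpoint keeps a regression model when small sample size is the stated reason for replacing logistic regression with frequency tables elsewhere.

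The cost is a sentence or two in the SAP and an option in the same SAS procedure, with no new data or visits. When there is an effect, the reported odds ratio will be slightly less favourable, and the interval will still be wide.
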